15.0 SPECIAL INSTRUCTIONS

15.1 Component Application, Review, and Participation

a. Application

The **S1415CD** Component Application is available on the protocol abstract page on the SWOG Website (www.swog.org) and the CTSU Member Website (<https://www.ctsu.org>). All interested SWOG, Alliance, NRG, and ECOG-ACRIN NCORP CCDR components must submit an application to be considered for participation. The purpose of the application is to verify that components will be able to fully meet the study requirements before attempting to open the trial. The application contains the component requirements and asks questions intended to determine component eligibility.

b. Review

Submitted applications will be carefully reviewed by the **S1415CD** Study Team before a component will be approved to participate. If necessary, additional questions may be asked of individual components during the application review period to help the **S1415CD** Study Team determine the feasibility of the trial at the particular location.

The **S1415CD** Study Team will inform components whether they have been approved for participation.

c. Participation

If a component is unable to continue participation in the protocol at any time while it is still actively accruing, the component must notify the **S1415CD** Study Team at [contact].

Components may begin recruiting to the trial after approval has been granted by the **S1415CD** Study Team and regulatory administration has been completed per [Section 13.2](#) and [Section 13.3](#).

15.2 Administration of Patient-Completed Questionnaires

- a. Patients are to complete questionnaires at registration (following consent and prior to or on the same day as initiation of systemic therapy), at the end of the first cycle of systemic therapy and by 6 months after registration. (See [Section 9.0](#) and [14.0](#) for the list of questionnaires and time points they are to be administered.) Questionnaires are anticipated to require 15-20 minutes to complete at each study time point.
- b. In order to minimize patient burden and streamline patient visits, it is preferable for questionnaires to be given to the patient at the clinic visit immediately prior to the clinician assessment; however, the study staff should accommodate the patient's preferences for filling out the questionnaires as described below. Questionnaires may be taken home and returned by mail to the component within \pm 1 week of the assessment timepoint.
- c. The research site should provide the patient with options for completing the questionnaires after the patient has reviewed them. The patient's review may help them decide if they need information they do not have with them at their visit or they may need assistance from a family member or caregiver.
- d. As a general reminder, review all completed questionnaires to be sure all of the questions have been answered and, when the patient is directed to mark only one response, that only one answer is marked. If the patient has marked more than one answer per question, ask which answer reflects how the patient is feeling. If the patient has skipped a question, tell the patient that a question was not answered and ask if the patient would like to answer the question. If the patient is unable to answer the question at the time of the visit, site staffs are encouraged to retain the questionnaire and contact the patient by phone to obtain outstanding information. If patient does not want to answer a particular question, the CRA will enter "Not answered by the patient" in Medidata RAVE®.
- e. Caregivers may assist patients with their questionnaires by administering the questionnaire orally to the patient, helping the patient find information and/or recording the patient's answers. Caregivers cannot answer for the patient unless the questionnaire specifically indicates that the caregiver may do so. For patients who are too sick to complete the questionnaires (even with assistance from the caregiver) or who are not able to come to a clinic visit (e.g. enrolled in hospice care), the CRA will record on the **S1415CD** Cover Sheet that the patient was too sick to complete the questionnaire.
- f. **S1415CD** Cover Sheet for Patient-Completed Questionnaires

For each time point, the nurse or CRA completes the **S1415CD** Cover Sheet for Patient-Completed Questionnaires. The Cover Sheet is submitted with the set of patient-completed forms at each scheduled assessment. The Cover Sheet is very important for tracking how and when the patient forms were completed. When a patient-completed form is not administered at a scheduled time point, it is important to know why the assessment did not occur; the form includes potential reasons for a patient not completing a form. All issues of noncompliance are noted on the **S1415CD** Cover Sheet.

15.3 Optional Training for Administration of Patient-Completed Questionnaires:

Anyone involved in the collection of quality of life data in SWOG trials should review the training program available on the SWOG website accessible from three locations. On the

SWOG Home Page (prior to member login), in the QUICKLINKS section on the bottom right corner of the page, there is a link to the Patient Reported Outcomes Training. The other two locations that the training is available are after SWOG member login on the CRA Workbench. The Training section and the New CRAs! Section both contain access to the Patient Reported Outcomes (PROs) training module. The training program is a narrated set of slides designed to standardize the way quality of life data is collected from patients. Questions regarding the quality of life assessments can be addressed to the SWOG Data Operations Office [contact]).

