- g. Patient adherence to PP-CSF prescription (clinical and patient report) at the end of the first cycle of systemic therapy: Proportion receiving PP-CSF among those for whom PP-CSF was ordered by the physician. The primary adherence measure will be obtained from the patient's chart as reported on the **S1415CD** CSF and Cancer Treatment form; secondary adherence will be measured via self-report on the **S1415CD** Follow-Up Patient Survey.
- h. Patient knowledge of PP-CSF indications, risks, benefits, and out-of-pocket costs (patient report): Evaluated using a patient survey capturing information on PP-CSF that is relevant to informed decision-making (i.e., knowledge of potential benefits, side effects, and short and long-term potential harms, out of pocket costs, and alternative approaches to therapy). Patient knowledge will be evaluated at baseline and at the end of the first cycle of systemic therapy using the **S1415CD** Baseline Patient Survey and the **S1415CD** Follow-Up Patient Survey. Out of pocket costs will be assessed by 6 months after registration based on self-report using the **S1415CD** Use and Copayment Survey.

i. Proportion completing initial systemic therapy regimen: a) at planned duration; b) at planned dose intensity (clinical): Records of early discontinuation or dose modification relative to the initially prescribed regimen will be captured on the **S1415CD** Discontinuation of Initial Systemic Therapy form and the **S1415CD** 12 Month Status Update.

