d. *Secondary Objective d: To compare patient knowledge of the indications for, efficacy of, and side effects associated with PP-CSF between the initiation and conclusion of the first cycle of myelosuppressive systemic therapy between patients registered at Intervention components versus Usual Care components.*

PP-CSF is only prescribed during the first cycle, so patient knowledge of PP-CSF will be evaluated as the change in knowledge between baseline and the end of the first cycle.

We will analyze change in the patient knowledge score between the initiation and conclusion of the first cycle of myelosuppressive systemic therapy, by fitting a linear mixed effects model with a time variable and an interaction between randomized group and time. We will use random effects to accommodate both the correlation among measures from the same patient as well as the correlation among patients from the same component. We will also adjust for component-level characteristics and patient-level clinical and demographic variables.

e. *Secondary Objective e: To compare the proportion of patients completing the initial systemic therapy regimen at planned duration and at planned dose intensity between patients registered at Intervention components versus Usual Care components.*

Patients are followed for 12 months; therapy status will be determined by 12 months.

Two separate mixed effects logistic models will be used to assess the effect of the intervention on completion of the initial systemic therapy regimen (i) at planned duration and (ii) at planned dose intensity. In addition to including an indicator variable for randomized group and a random effect for component, we will adjust for component- level characteristics and patient-level clinical and demographic variables.

f. *Secondary Objective f: To compare antibiotic use both as prophylaxis and as treatment for FN between patients registered at Intervention components versus Usual Care components.*

Antibiotic use as prophylaxis for FN and as a treatment for FN is relevant during the first cycle when PP-CSF may be administered. To adequately cover all antibiotic use that may be related to prophylaxis and treatment of FN, antibiotic prescriptions for the first 30 days of systemic treatment will be evaluated.

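### The questionnaire rules make no exception for the PP-CSF knowledge surveys, so the Secondary Objective d score may mix what patients know with looked-up or assisted answers

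*Combined protocol and SAP*

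**What the plan says.** Section 15.2 governs all patient-completed questionnaires and refers to Sections 9.0 and 14.0 for the list. The relevant rules are these:

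- **15.2b:** in-clinic completion just before the clinician assessment is preferred, but staff should accommodate the patient's preference. "Questionnaires may be taken home and returned by mail to the component within" one week either side of the timepoint.
- **15.2c:** "The research site should provide the patient with options for completing the questionnaires after the patient has reviewed them". The preview "may help them decide if they need information they do not have with them at their visit".
- **15.2d:** if a patient cannot answer an item at the visit, staff are encouraged to keep the form and phone the patient for the outstanding answer.
- **15.2e:** caregivers may assist by "administering the questionnaire orally to the patient, helping the patient find information", and by writing down answers. The limit is that "Caregivers cannot answer for the patient unless the questionnaire specifically indicates that the caregiver may do so".
- **15.2f:** a Cover Sheet goes in with each set of forms and tracks how and when they were completed.

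The knowledge endpoint in Section 10.1h is "Evaluated using a patient survey capturing information on PP-CSF that is relevant to informed decision-making", using the Baseline Patient Survey and the Follow-Up Patient Survey. For the analysis, Section 11.3d says: "We will analyze change in the patient knowledge score between the initiation and conclusion of the first cycle". The model is a linear mixed model with a group-by-time interaction.

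**The concern.** For a form that asks about bills or medical history, looking something up improves the answer. For a knowledge item it changes the quantity being measured: a patient who cannot state what PP-CSF is for has given a valid answer, and it is the one the endpoint needs. The 15.2d call-back treats that answer as missing data to be recovered. The bar on caregivers answering for the patient does not stop a caregiver from finding the answer and handing it over.

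The interpretation of Secondary Objective d is at stake. If some patients in both arms arrive at the same looked-up answers, a real difference in knowledge gain shrinks. A null result would then be harder to read, because it could reflect no effect or partly shared sources.

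**Working it through.** **Text check.** Four questions decide whether the rules reach the knowledge score.

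1. *Are the two surveys covered?* Yes. Both are listed under patient questionnaires in Section 9.0 and again in Section 14.4, the lists to which 15.2a refers.
2. *Do they carry the knowledge score?* Yes, by 10.1h. Section 1.2d defines the objective as knowledge of indications, efficacy and side effects, none of which needs the patient's own documents. The form that does need documents is the Use and Copayment Survey (Section 9.0, note 3), a separate form due by Month 6.
3. *Does any text require unaided completion of the knowledge items?* None was found.
4. *Does the analysis allow for mode or help?* No. Section 11.3d adjusts for component-level characteristics and patient-level clinical and demographic variables, with no term or sensitivity analysis for place of completion or assistance.

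**Size.** Section 11.1 covers Primary Objectives a, b and c only. It states no power, effect size or SD for Secondary Objective d, so there is no plan figure to reproduce. The following uses assumed inputs.

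*Equal look-up, same final score.* Suppose a share q of patients in both arms looks up answers at follow-up and reaches the same mean S, with equal baseline means. The follow-up mean in an arm with true mean μ is (1−q)μ + qS, so the between-arm difference in change becomes (1−q) times the true one. For a comparison that would have had 80% power at two-sided 5% (an assumed starting point), power = Φ(2.80(1−q) − 1.96), and the sample needed for equal power is multiplied by 1/(1−q)².

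| q | Share of true difference kept | Power | Sample multiplier |
|---|---|---|---|
| 10% | 0.90 | Φ(0.56) = 71% | 1.23 |
| 20% | 0.80 | Φ(0.28) = 61% | 1.56 |
| 30% | 0.70 | Φ(0.00) = 50% | 2.04 |

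*Equal look-up, equal added gain.* If look-up instead adds the same amount g for every such patient in either arm, each arm's change rises by qg and the interaction contrast is unaffected.

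*Unequal look-up.* The bias is (difference in share) × g. With an assumed difference of 5 to 20 percentage points and g of 0.5 to 1.0 SD, it runs from 0.05 × 0.5 = 0.025 SD to 0.20 × 1.0 = 0.20 SD. For scale, take the planned 2,160 against 720 patients, 90 per component, all with both surveys. The difference detectable with 80% power is (1.96 + 0.84) × √[DEFF × (1/720 + 1/2160)], with DEFF = 1 + 89 × ICC:

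| ICC | DEFF | Detectable difference |
|---|---|---|
| 0 | 1.00 | 0.12 SD |
| 0.01 | 1.89 | 0.17 SD |
| 0.02 | 2.78 | 0.20 SD |
| 0.05 | 5.45 | 0.28 SD |

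The plan uses an ICC of 0.02 for FN and gives none for the knowledge score.

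**The case against.** The strongest reply is that nothing tells patients to look up PP-CSF answers. In-clinic completion is preferred, caregivers may not answer for the patient, and help with finding information most naturally means bills or records. The survey forms and the Cover Sheet are not in the documents. The forms may already ask for unaided answers or offer a don't-know option, and the Cover Sheet may already record place and help. The rules are also the same in every arm.

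Much of this stands. A reader might infer that Secondary Objective d scores an open-book test in place of knowledge. The documents do not support that: look-up is permitted, not directed, and its frequency is unknown. A reader might also infer that more look-up at follow-up, where forms can go home, would create a false intervention effect. It would not. A gain common to both arms raises the within-arm change but cancels in the group-by-time test, and the documents give no reason to expect look-up to differ by arm.

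The reply does not remove the gap. The preference for in-clinic completion yields to patient preference. The wording about finding information is not confined to the cost survey. The call-back rule applies to any unanswered item. Section 11.3d makes no use of what the Cover Sheet records.

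**Conclusion.** The concern holds in a limited form. Section 15.2b to 15.2e permits look-up, content help and later recovery of answers for the two surveys that measure PP-CSF knowledge, so the score is not protected as a measure of what patients know. The extent of contamination is unknown.

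The likely consequence is dilution of the group-by-time contrast. That rests on look-up being similar in both arms and bringing patients to similar scores. Between-arm bias requires look-up that differs by arm. The power and bias figures show only how the effect scales with assumed inputs; they do not estimate a loss in this trial.

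This is one of nine secondary objectives and no primary objective is affected. The change is still worth making because it is small and specific.

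**What to change.** In 15.2c, 15.2d and 15.2e, state that the PP-CSF knowledge items of the Baseline and Follow-Up Patient Surveys are answered by the patient without looking up information, without help on content, and without a later call-back to obtain an answer. Completion in clinic is preferred, and a don't-know response is accepted. Reading items aloud and writing down the patient's answers stay allowed. The rules for all other forms stay as they are.

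Use the Cover Sheet to record place of completion and any content help, adding an item if it does not already capture these, and report both by arm. Any repeat of the 11.3d analysis should be labelled exploratory. It should exclude only surveys completed at home or with content help, not those merely read aloud or transcribed. It should also say that this is selection on a post-randomisation variable, which may be related to illness, literacy or language.

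The cost is a few sentences, possibly one Cover Sheet item, and perhaps a few more unanswered or don't-know items. Protocol pages carry a closed stamp effective 04/15/2020, so the change in administration may reach few if any surveys. Reporting by arm and the exploratory repeat remain possible where the Cover Sheet already holds the information.

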16.0 ETHICAL AND REGULATORY CONSIDERATIONS

The following must be observed to comply with Food and Drug Administration regulations for the conduct and monitoring of clinical investigations; they also represent sound research practice:

Informed Consent

The principles of informed consent are described by Federal Regulatory Guidelines (Federal Register Vol. 46, No. 17, January 27, 1981, part 50) and the Office for Protection from Research Risks Reports: Protection of Human Subjects (Code of Federal Regulations 45 CFR 46). They must be followed to comply with FDA regulations for the conduct and monitoring of clinical investigations.

Institutional Review

This study must be approved by an appropriate institutional review committee as defined by Federal Regulatory Guidelines (Ref. Federal Register Vol. 46, No. 17, January 27, 1981, part 56) and the Office for Protection from Research Risks Reports: Protection of Human Subjects (Code of Federal Regulations 45 CFR 46).

Monitoring

This study will be monitored by the Clinical Data Update System (CDUS) Version 3.0. Cumulative, abbreviated CDUS data will be submitted quarterly to CTEP by electronic means. Reports are due January 31, April 30, July 31 and October 31.

Confidentiality

Please note that the information contained in this protocol is considered confidential and should not be used or shared beyond the purposes of completing protocol requirements until or unless additional permission is obtained.

Adverse Events

16.1 Adverse Event Reporting Requirements

a. Purpose

Adverse event data collection and reporting, which are required as part of every clinical trial, are done to ensure the safety of patients enrolled in the studies as well as those who will enroll in future studies using similar agents. Adverse events are reported in a routine manner at scheduled times during a trial. (Directions for routine reporting are provided in [Section 14.0](#).) Additionally, certain adverse events must be reported in an expedited manner to allow for more timely monitoring of patient safety and care. The following guidelines prescribe expedited adverse event reporting for this protocol.

b. Reporting method

This study requires that expedited adverse events be reported using the Cancer Therapy Evaluation Program Adverse Event Reporting System (CTEP-AERS). CTEP's guidelines for CTEP-AERS can be found at <http://ctep.cancer.gov>. A CTEP-AERS report must be submitted to the SWOG Operations Office electronically via the CTEP-AERS Web-based application located at http://ctep.cancer.gov/protocolDevelopment/electronic_applications/adverse_events.htm.

In the rare event when internet connectivity is disrupted an electronic report MUST be submitted immediately upon re-establishment of internet connection.

c. When to report an event in an expedited manner

When the adverse event requires expedited reporting, submit the report within 10 calendar days of learning of the event.

d. Other recipients of adverse event reports

The SWOG Operations Office will forward reports and documentation to the appropriate regulatory agencies and drug companies as required.

Adverse events determined to be reportable to the Institutional Review Board responsible for oversight of the patient must be reported according to local policy and procedures.

e. Expedited reporting for commercial agents

Commercial reporting requirements are provided in [Table 16.1](#) and are limited to the commercial agent(s) of interest. The commercial agents for this study are Colony Stimulating Factors (CSFs). If there is any question about the reportability of an adverse event or if on-line CTEP-AERS cannot be used, please telephone or email the SAE Program at the Operations Office, [name] or [contact], before preparing the report.

Table 16.1. Expedited reporting requirements for adverse events experienced by patients using CSFs within 30 days of the last administration of the CSF.

ATTRIBUTION	Grade 4		Grade 5 ^a	
	Unexpected	Expected	Unexpected	Expected
Unrelated or Unlikely			CTEP-AERS	CTEP-AERS
Possible, Probable, Definite	CTEP-AERS		CTEP-AERS	CTEP-AERS
CTEP-AERS: Indicates an expedited report is to be submitted via CTEP-AERS within 10 calendar days of learning of the event ^b .				

^a This includes all deaths within 30 days of the last dose of treatment with a commercial agent(s), regardless of attribution. Any death that occurs more than 30 days after the last dose of treatment with a commercial agent(s) and is attributed (possibly, probably, or definitely) to the agent(s) and is not due to cancer recurrence must be reported according to the instructions above.

^b Submission of the on-line CTEP-AERS report plus any necessary amendments generally completes the reporting requirements. You may, however, be asked to submit supporting clinical data to the Operations Office in order to complete the evaluation of the event. If requested, the specified data should be sent within 5 calendar days by fax to [contact].

f. Reporting Pregnancy, Fetal Death, and Death Neonatal

1. **Pregnancy** Study participants who become pregnant while on study; that pregnancy should be reported in an expedited manner via CTEP-AERS as **Grade 3 “Pregnancy, puerperium and perinatal conditions – Other (pregnancy)”** under the **Pregnancy, puerperium and perinatal conditions** SOC.

Additionally, the pregnancy outcome for patients on study should be reported via CTEP-AERS at the time the outcome becomes known, accompanied by the same Pregnancy Report Form used for the initial report.

2. **Fetal Death** Fetal Death defined in CTCAE as “A disorder characterized by death in utero; failure of the product of conception to show evidence of respiration, heartbeat, or definite movement of a voluntary muscle after expulsion from the uterus, without possibility of resuscitation” should be reported expeditiously as **Grade 4 “pregnancy, puerperium and perinatal conditions – Other (pregnancy loss)”** under the **Pregnancy, puerperium and perinatal conditions** SOC.
3. **Death Neonatal** Neonatal death, defined in CTCAE as “A disorder characterized by cessation of life occurring during the first 28 days of life” that is felt by the investigator to be at least possibly due to the investigational agent/intervention should be reported expeditiously.

A neonatal death should be reported expeditiously as **Grade 4 “General disorders and administration – Other (neonatal loss)”** under the **General disorders and administration** SOC.

*Fetal death and neonatal death should **NOT** be reported as a Grade 5 event. If reported as such, the CTEP-AERS interprets this as a death of the patient being treated.*

NOTE: When submitting CTEP-AERS reports for "Pregnancy", "Pregnancy loss", or "Neonatal loss", the Pregnancy Information Form should also be completed and faxed with any additional medical information to [contact]. The potential risk of exposure of the fetus to the investigational agent(s) or chemotherapy agent(s) should be documented in the "Description of Event" section of the CTEP-AERS report.

The Pregnancy Information Form is available at:
http://ctep.cancer.gov/protocolDevelopment/adverse_effects/htm.

CLOSED EFFECTIVE 04/15/2020

